11.8 Adverse events of special interest

The following adverse events are considered adverse events of special interest (Table 8) and potential immune-mediated disorders (Table 9).

Table 8 Adverse events of special interest

Immunologic	Anaphylaxis	
Neurological	Isolated anosmia/ageusia*	Meningoencephalitis
	Guillain-Barre Syndrome	Peripheral facial nerve palsy
	Acute disseminated	Generalised convulsion
	encephalomyelitis (ADEM)	Myelitis
	Aseptic meningitis	

Haematological	Thrombosis** Stroke Thrombocytopenia (G3 or above) Eosinophilia	Coagulation disorder (includes coagulopathy, thrombosis, thromboembolism, internal/external bleed and stroke)
Cardiac	Acute cardiovascular injury (includes myocarditis, pericarditis, arrhythmias, heart failure, infarction)	
Dermatological	Chilblain-like lesions Single organ cutaneous vasculitis	Erythema multiforme Alopecia
Gastrointestinal	Acute liver injury	Appendicitis
Respiratory	ARDS	
Renal	Acute kidney injury	

**In the absence of COVID-19*

*** Excluding superficial thrombophlebitis (including line-associated)*

Table 9 List of potential immune-mediated diseases (pIMDs)

Medical Concept	Additional Notes
Blood disorders and coagulopathies	
Antiphospholipid syndrome	
Autoimmune aplastic anemia	
Autoimmune hemolytic anemia	
 Includes warm antibody hemolytic anemia and cold antibody hemolytic anemia

Autoimmune lymphoproliferative syndrome (ALPS)	
Autoimmune neutropenia	
Autoimmune pancytopenia	
Autoimmune thrombocytopenia	
 Frequently used related terms include: “autoimmune thrombocytopenic purpura”, “idiopathic thrombocytopenic purpura (ITP)”, “idiopathic immune thrombocytopenia”, “primary immune thrombocytopenia”.
Evans syndrome	
Pernicious anemia	
Thrombosis with thrombocytopenia syndrome (TTS)	
Thrombotic thrombocytopenic purpura	
 Also known as “Moschowitz-syndrome” or “microangiopathic hemolytic anemia”
Cardio-pulmonary inflammatory disorders	
Idiopathic Myocarditis/Pericarditis	
Including but not limited to:
 
 Autoimmune / Immune-mediated myocarditis Autoimmune / Immune-mediated pericarditis Giant cell myocarditis
Idiopathic pulmonary fibrosis	Including but not limited to:

	
 • Idiopathic interstitial pneumonia (frequently used related terms include “Interstitial lung disease”, “Pulmonary fibrosis”, “Immune-mediated pneumonitis”) • Pleuroparenchymal fibroelastosis (PPFE)
Pulmonary alveolar proteinosis (PAP)	
 • Frequently used related terms include: “pulmonary alveolar lipoproteinosis”, “phospholipidosis”
Endocrine disorders	
Addison’s disease	
Autoimmune / Immune-mediated thyroiditis	
Including but not limited to:
 
 • Hashimoto thyroiditis (autoimmune hypothyroidism, lymphocytic thyroiditis) • Atrophic thyroiditis • Silent thyroiditis • Thyrotoxicosis

Autoimmune diseases of the testis and ovary	
 Includes autoimmune oophoritis, autoimmune ovarian failure and autoimmune orchitis
Autoimmune hyperlipidemia	
Autoimmune hypophysitis	
Diabetes mellitus type I	
Grave's or Basedow's disease	
 Includes Marine Lenhart syndrome and Graves' ophthalmopathy, also known as thyroid eye disease (TED) or endocrine ophthalmopathy
Insulin autoimmune syndrome	
Polyglandular autoimmune syndrome	
 Includes Polyglandular autoimmune syndrome type I, II and III
Eye disorders	
Ocular Autoimmune / Immune-mediated disorders	
Including but not limited to:
 
 Acute macular neuroretinopathy (also known as acute macular outer retinopathy) Autoimmune / Immune-mediated retinopathy Autoimmune / Immune-mediated uveitis, including idiopathic uveitis and sympathetic ophthalmia Cogan's syndrome: an oculo-audiovestibular disease Ocular pemphigoid Ulcerative keratitis

	
 • Vogt-Koyanagi-Harada disease
Gastrointestinal disorders	
Autoimmune / Immune-mediated pancreatitis	
Celiac disease	
Inflammatory Bowel disease	
Including but not limited to:
 
 • Crohn's disease • Microscopic colitis • Terminal ileitis • Ulcerative colitis • Ulcerative proctitis
Hepatobiliary disorders	
Autoimmune cholangitis	
Autoimmune hepatitis	
Primary biliary cirrhosis	
Primary sclerosing cholangitis	
Musculoskeletal and connective tissue disorders	
Gout	
 • Includes gouty arthritis
Idiopathic inflammatory myopathies	
Including but not limited to:
 
 • Dermatomyositis

	
 • Inclusion body myositis • Immune-mediated necrotizing myopathy • Polymyositis
Mixed connective tissue disorder	
Polymyalgia rheumatica (PMR)	
Psoriatic arthritis (PsA)	
Relapsing polychondritis	
Rheumatoid arthritis	
Including but not limited to:
 
 • Rheumatoid arthritis associated conditions • Juvenile idiopathic arthritis • Palindromic rheumatism • Still's disease • Felty's syndrome
Sjögren's syndrome	
Spondyloarthritis	
Including but not limited to:
 
 • Ankylosing spondylitis • Juvenile spondyloarthritis • Keratoderma blenorrhagica • Psoriatic spondylitis

	
 • Reactive Arthritis (Reiter's Syndrome) • Undifferentiated spondyloarthritis
Systemic Lupus Erythematosus	
 • Includes Lupus associated conditions (e.g. Cutaneous lupus erythematosus, Lupus nephritis, etc.) or complications such as shrinking lung syndrome (SLS)
Systemic Scleroderma (Systemic Sclerosis)	
 • Includes Reynolds syndrome (RS), systemic sclerosis with diffuse scleroderma and systemic sclerosis with limited scleroderma (also known as CREST syndrome)
Neuroinflammatory/neuromuscular disorders	
Acute disseminated encephalomyelitis (ADEM) and other inflammatory demyelinating variants	
Includes the following:
 
 • Acute necrotising myelitis • Bickerstaff's brainstem encephalitis • Disseminated necrotizing leukoencephalopathy (also known as Weston-Hurst syndrome, acute hemorrhagic leuko-encephalitis, or acute necrotizing hemorrhagic encephalomyelitis) • Myelin oligodendrocyte glycoprotein antibody-associated disease • Neuromyelitis optica (also known as Devic's disease) • Noninfective encephalitis / encephalomyelitis / myelitis • Postimmunization encephalomyelitis

Guillain-Barré syndrome (GBS)	
 • Includes variants such as Miller Fisher syndrome and the acute motor and sensory axonal neuropathy (AMSAN)
Idiopathic cranial nerve palsies/paresis and inflammations (neuritis)	
Including but not limited to:
 
 • Cranial nerve neuritis (e.g. Optic neuritis) • Idiopathic nerve palsies/paresis (e.g. Bell's palsy) • Melkersson-Rosenthal syndrome • Multiple cranial nerve palsies/paresis
Multiple Sclerosis (MS)	
Includes the following:
 
 • Clinically isolated syndrome (CIS) • Malignant MS (the Marburg type of MS) • Primary-progressive MS (PPMS) • Radiologically isolated syndrome (RIS) • Relapsing-remitting MS (RRMS) • Secondary-progressive MS (SPMS) • Uhthoff's phenomenon
Myasthenia gravis	
 • Includes ocular myasthenia and Lambert-Eaton myasthenic syndrome
Narcolepsy	
 • Includes narcolepsy with or without presence of unambiguous cataplexy

Peripheral inflammatory demyelinating neuropathies and plexopathies
	
Including but not limited to:
 
 • Acute Brachial Radiculitis (also known as Parsonage-Turner Syndrome or neuralgic amyotrophy) • Antibody-mediated demyelinating neuropathy • Chronic idiopathic axonal polyneuropathy (CIAP) • Chronic Inflammatory Demyelinating Polyradiculoneuropathy (CIDP), including atypical CIDP variants (e.g. multifocal acquired demyelinating sensory and motor neuropathy also known as Lewis-Sumner syndrome) • Multifocal motor neuropathy (MMN)

Transverse myelitis (TM)
	
 • Includes acute partial transverse myelitis (APTM) and acute complete transverse myelitis (ACTM)

Renal disorders
	

Autoimmune / Immune-mediated glomerulonephritis
	
Including but not limited to:
 
 • IgA nephropathy • IgM nephropathy • C1q nephropathy • Fibrillary glomerulonephritis • Glomerulonephritis rapidly progressive • Membranoproliferative glomerulonephritis • Membranous glomerulonephritis

	
 • Mesangioproliferative glomerulonephritis • Tubulointerstitial nephritis and uveitis syndrome
Skin and subcutaneous tissue disorders	
Alopecia areata	
Autoimmune / Immune-mediated blistering dermatoses	
Including but not limited to:
 
 • Bullous Dermatitis • Bullous Pemphigoid • Dermatitis herpetiformis • Epidermolysis bullosa acquisita (EBA) • Linear IgA-mediated bullous dermatosis (LABD), also known as Linear IgA disease • Pemphigus
Erythema multiforme	
Erythema nodosum	
Reactive granulomatous dermatitis	
Including but not limited to
 
 • Interstitial granulomatous dermatitis • Palisaded neutrophilic granulomatous dermatitis
Lichen planus	
 • Includes liquen planopilaris
Localised Scleroderma (Morphoea)	
 • Includes Eosinophilic fasciitis (also called Shulman syndrome)
Psoriasis	

Pyoderma gangrenosum	
Stevens-Johnson Syndrome (SJS)	Including but not limited to: 
 • Toxic Epidermal Necrolysis (TEN) • SJS-TEN overlap
Sweet's syndrome	
 • Includes Acute febrile neutrophilic dermatosis
Vitiligo	
Vasculitis	
Large vessels vasculitis	Including but not limited to: 
 • Arteritic anterior ischemic optic neuropathy (AAION or arteritic AION) • Giant cell arteritis (also called temporal arteritis) • Takayasu's arteritis
Medium sized and/or small vessels vasculitis	Including but not limited to: 
 • Anti-neutrophil cytoplasmic antibody (ANCA) positive vasculitis (type unspecified) • Behcet's syndrome • Buerger's disease (thromboangiitis obliterans) • Churg–Strauss syndrome (allergic granulomatous angiitis) • Erythema induratum (also known as nodular vasculitis) • Henoch-Schonlein purpura (also known as IgA vasculitis) • Microscopic polyangiitis

	
 • Necrotizing vasculitis • Polyarteritis nodosa • Single organ cutaneous vasculitis, including leukocytoclastic vasculitis, hypersensitivity vasculitis and acute hemorrhagic edema of infancy (AHEI) • Wegener's granulomatosis
Other (including multisystemic)	
Anti-synthetase syndrome	
Capillary leak syndrome	
 • Frequently used related terms include : “systemic capillary leak syndrome (SCLS)” or “Clarkson's Syndrome”
Goodpasture syndrome	
 • Frequently used related terms include : “pulmonary renal syndrome” and “anti-Glomerular Basement Membrane disease (anti-GBM disease)”
Immune-mediated enhancement of disease	
 • Includes vaccine associated enhanced disease (VAED and VAERD). Frequently used related terms include “vaccine-mediated enhanced disease (VMED)”, “enhanced respiratory disease (ERD)”, “vaccine-induced enhancement of infection”, “disease enhancement”, “immune enhancement”, and “antibody-dependent enhancement (ADE)
Immunoglobulin G4 related disease	
Langerhans' cell histiocytosis	

Multisystem inflammatory syndromes	Including but not limited to: 
 • Kawasaki’s disease • Multisystem inflammatory syndrome in adults (MIS-A) • Multisystem inflammatory syndrome in children (MIS-C)
Overlap syndrome	
Raynaud’s phenomenon	
Sarcoidosis	
 • Includes Loefgren syndrome
Susac's syndrome	

12. Trial methods

12.1 Source data

Outcome data will be collected using a purpose-designed database. Where the trial database is the site of original recording this will be considered source data. Data will be captured at each trial visit (see Table 4 for schedule of data collection). Volunteers and participants will enter data directly into the screening and trial databases. These will be the source data for these responses.

Where the database is not the original recording the source data will include, but is not limited to medical history, medication records, vital signs, physical examination records, urine assessments, blood results, and details of vaccinations.

12.2 Planned recruitment rate

Anticipated rate of enrolment:

We will recruit 960 participants at approximately 15 sites over a 6 month period. For the first 50 participants recruited to Groups 4 and 5 there will be real time safety monitoring. Once the first 50 participants in Groups 4 and 5 reach visit 3, then a safety review will take place and will include data up to 30 days after the second vaccination point. Recruitment to the study will continue during the safety review but will pause if there are any safety concerns.

12.3 Participant recruitment

The public will be made aware of the trial via:

- Press announcements
- On a website
- Social media
- Notification via the National Vaccines Studies Register
- Notification via vaccination centres
- Contact from their direct care team (e.g. the GP practice responsible for their vaccinations)
- Be Part of Research Volunteer Service
 - The purpose of the Be Part of Research Volunteer Service (BPORVS) is to allow members of the public to become volunteers by creating an account, specifying the areas of research that they are interested in and give consent to be contacted by the Be Part of Research team. Those who consent will receive information about BPORVS, in particular to alert them to specific BPORVS registered studies that they may be interested in, based on their volunteered details and study specific eligibility criteria, using an online self-registration service. The register is

open to those that live in the UK, are over 18 and have an email address. At the time of registration, volunteers are made aware that they are not signing up to take part in a specific health study when they join this register and that they will only be signposted to studies that have NIHR funding or are listed on the NIHR CRN Portfolio. If the volunteer is interested in the study there will be a link in the email to take them to the study team (e.g. website, pre-screener) where they will move into the study teams screening process and consenting process if they take part in the study. The Be Part of Research Volunteer Service is funded by the Department of Health and Social Care and delivered by the National Institute for Health and Care Research (NIHR) in conjunction with Public Health Agency, Research & Development, Northern Ireland, NHS Scotland and Health and Care Research Wales. Further information on the Be Part of Research Volunteer Service is available here: <https://bepartofresearch.nihr.ac.uk/volunteer-service/researcher>

- Charities via social media, websites and newsletters as well as sending study information to individuals who have expressed as interest of being informed of research opportunities relevant to them.

Volunteers interested in joining the trial will be directed to a 2-stage online screening process using a purpose-designed website hosted by the University of Bristol and approved by the Research Ethics Committee (REC). The REC-approved participant information leaflet (PIL) will be available via this website to download. A REC-approved video presentation of the PIL may be made available for volunteers to access remotely.

Study sites will access the details of volunteers in their local area and will follow the process outlined in Section 5.8. Direct care teams can contact potential volunteers directly without prior registration on the website, as described in section 5.8.

Prior to consent volunteers will have an opportunity to discuss the trial with a member of the research team, who will answer any questions and take written informed consent if the volunteer decides to participate. The volunteer will be given an explanation of the exact nature of the trial, what it involves for the participant, implications and constraints of the protocol, known side effects and any risks involved in taking part, and that anonymised samples taken during the trial may be shared for future research. The consent form will include permission to inform their GP of their participation and optional consent to allow indefinite storage of any leftover samples for use in other ethically approved research. A copy of the signed informed consent form will be given to the participant.

The voluntary nature of participation and that the participant can stop active participation at any time will be emphasised. It will also be explained that participants will not be exempt from following the contemporaneous government COVID-19 guidance to minimise viral transmission.

12.4 Discontinuation of vaccinations or active trial participation of participants

Each participant has the right to stop active participation at any time for any reason and is not obliged to give their reasons for doing so. Data and samples collected prior to the change in status will be retained and reported.

A clinician may decline trial vaccinations for a participant at any time if they feel it is in the participant's best interests (e.g., due to ineligibility, either arising during the trial or

retrospectively having been overlooked at screening, significant protocol deviation, participant non-compliance with trial requirements, adverse event which requires discontinuation of the trial involvement or results in inability to continue to comply with trial procedures, administrative reason).

Reasons for all discontinuations will be captured in the trial database and reported.

The DMSC may recommend cessation of treatment for participants.

12.5 Frequency and duration of follow up

Participants are followed up for 5 months from enrolment and randomisation. Pregnant women will be followed-up to delivery.

12.6 Likely rate of loss to follow-up

With a short period of participation of 6 months loss to follow-up is expected to be minimal (less than 5%).

12.7 Expenses

Volunteers will be compensated for their time, the inconvenience of having blood tests and procedures, and their travel expenses. The total amount compensated will depend on the exact number of visits, and whether any repeat or additional visits are necessary. For all trial visits participants will be compensated up to £45 per visit (total compensation for completing trial would be £90 for a subset of participants in groups in group 3 and up to £270 for all other participants).

13. Statistics

13.1 Sample size calculation

Sample size calculations have been performed to test all primary immunogenicity objectives in both part A and part B of the trial. All sample size calculations were performed using the SSI module in Stata.⁹

Part A: Assessment of co-administration of COVID-19 vaccine and RZV

We hypothesise that (1) immunogenicity (anti-S protein Ig concentrations, both Original and Omicron strains) of concomitant administration of C19 and RZV (first or second dose) will be non-inferior to C19 alone, and (2) immunogenicity (anti-gE Ig concentrations) of concomitant administration of RZV (first or second dose) and C19 will be non-inferior to RZV alone.

The power calculations to test hypotheses in part A are provided in Table 10.

Table 10 Sample size estimates for part A

Outcome	Sample size excluding 10% inflation for dropout	SD (log10 scale)	Assumed true GMR	Non-inferiority margin (log10 scale)	Power for each outcome	Conjunctive power for part A
Anti-S Ig	95	0.35	1	0.174	92.9%	80.1%
Anti-gE Ig	95	0.35	1	0.174	92.9%	

A sample size of 106 per group will provide 80% power to test all part A hypotheses using a 2.5% one-sided significance level and allowing for 10% dropout.

Part B: Assessment of co-administration of adjuvanted influenza vaccine and RZV

We hypothesise that (1) immunogenicity (for 3 of the strains included in the vaccine; HAI influenza A H3N2, HAI influenza A H1N1 and HAI influenza B Victoria) of concomitant administration of aQIV and RZV (first or second dose) will be non-inferior to aQIV alone, and (2) immunogenicity (anti-gE Ig concentrations) of concomitant administration of RZV (first or second dose) and aQIV will be non-inferior to RZV alone.

The power calculations to test hypotheses in part B are presented in Table 11.

Table 11 Sample size estimates for part B

Outcome	Sample size excluding 10% inflation for dropout	SD (log10 scale)	Assumed true GMR	Non-inferiority margin (log10 scale)	Power for each outcome	Conjunctive power for correlated outcomes (HAI)*	Conjunctive power for part B
HAI influenza A H3N2	216	0.45	1	0.174	98.0%		
HAI influenza A H1N1	216	0.54	1	0.174	91.8%	80.7%	80.6%
HAI influenza B Victoria	216	0.57	1	0.174	88.7%		
Anti-gE Ig	216	0.35	1	0.174	99.93%	-	

* Estimated using correlation matrix from ComFluCOV HAI data; conjunctive power for HAI outcomes was calculated using R.

A sample size of 240 per group will provide 80% power to test all part B hypotheses using a 2.5% one-sided significance level and allowing for 10% dropout.

Final sample size justification

A sample size of 960 (120 into groups 1 and 2, 240 into groups 3-5, after inflating to fit a 1:1:2:2:2 allocation ratio) will allow us to adequately assess all primary immunogenicity objectives.

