4.1 Primary outcome

Part A: Assessment of co-administration of COVID-19 and RZV

Co-Primary Endpoints

1) Immunogenicity of C19

Anti-S protein Ig concentrations expressed as Geometric Mean Concentrations (GMCs) for both strains in C19 vaccine/RZV (first or second dose, groups 2 & 3) and C19 vaccine alone (group 1), will be used to calculate between group ratios expressed a geometric mean ratio (GMR), at 1 month after vaccination with C19 vaccine.

2) Immunogenicity of RZV

Anti-gE Ig concentrations expressed as GMCs after co-administration of C19 vaccine/RZV (first or second dose) and RZV alone, 1 month after 2nd dose of RZV, and between-group ratios expressed as GMRs.

Success criteria:

Part A of the trial will be classified as a success if both of the following meet the success criteria:

- 1) The combined administration of C19 vaccine and RZV (first or second dose) will be considered non-inferior to C19 vaccine alone if the lower limit of the 95% confidence interval for the (GMR) of anti-S protein Ig concentrations exceeds 0.67, the standard WHO non-inferiority margin for recommendation of new vaccines.⁷, AND

2) The combined administration of C19 vaccine and RZV (first or second dose) will be considered non-inferior to RZV alone if the lower limit of the 95% confidence interval for the GMR of Anti-gE Ig concentrations exceeds 0.67.

3) Safety of RZV

The rate of grade 3 and 4 solicited systemic adverse reactions (Table 2) after C19 vaccine/RZV (first or second dose, groups 2 and 3) and RZV alone 7 days after vaccination (groups 1-5) This is a descriptive outcome.

Table 2 Solicited AEs collected on post vaccination diary cards

Systemic solicited AEs
Fatigue
Fever
GI symptoms†
Headache
Myalgia
Shivering

†Gastrointestinal symptoms include nausea, vomiting, diarrhoea and/or abdominal pain

Note: The above AEs are assumed to be related and will be classed as adverse reactions.

Part B: Assessment of co-administration of adjuvanted influenza vaccine and RZV

Co-Primary Endpoints

1) Immunogenicity of aQIV

HAI titres expressed as GMCs in aQIV/RZV (first or second dose, groups 4 & 5) and aQIV alone (group 3) will be used to calculate between group ratios, expressed as GMR at one month after aQIV vaccination.

2) Immunogenicity of RZV

Anti-gE Ig concentrations expressed as GMCs after co-administration of aQIV/RZV (first or second dose) and RZV alone, 1 month after 2nd dose of RZV, and between-group ratios expressed as GMRs.

Success criteria:

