Part B of the trial will be classified as a success if both of the following meet the success criteria:

- 1) The combined administration of aQIV and RZV (first or second dose) will be considered non-inferior to aQIV (for 3 of the strains included in the vaccine; HAI influenza A H3N2, HAI influenza A H1N1 and HAI influenza B Victoria) alone if the lower limit of the 95% confidence interval for the GMR of HAI exceeds 0.67, the standard WHO non-inferiority margin for recommendation of new vaccines.⁷, AND
- 2) The combined administration of aQIV and RZV (first or second dose) will be considered non-inferior to RZV alone if the lower limit of the 95% confidence interval for the GMR of Anti-gE Ig concentrations exceeds 0.67.

3) Safety of RZV

The rate of grade 3 and 4 solicited systemic adverse reactions (Table 2) after aQIV/RZV (first or second dose, groups 4 and 5) and RZV alone 7 days after vaccination (groups 1-5). This is a descriptive outcome.

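### The primary success rule does not say how the two co-administration schedules in each part combine, and the stated 80% power covers only one of them

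*Protocol*

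**What the plan says.** The Part A rule in section 4.1 reads "The combined administration of C19 vaccine and RZV (first or second dose) will be considered non-inferior to C19 vaccine alone" if the lower 95% limit of the GMR exceeds 0.67. A parallel criterion for anti-gE must also be met. Part B has the same form: "The combined administration of aQIV and RZV (first or second dose) will be considered non-inferior to aQIV" alone, for three HAI strains, again with an anti-gE criterion.

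Section 4.1 identifies the co-administration groups as 2 and 3 against Group 1 for anti-S, and 4 and 5 against Group 3 for HAI. Table 3 in section 5.5 shows that these are distinct randomised schedules, with the second vaccine given alongside either the first or the second RZV dose.

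Section 13.1 makes the power claims: "A sample size of 106 per group will provide 80% power to test all part A hypotheses using a 2.5% one-sided significance level" for Part A and "A sample size of 240 per group will provide 80% power to test all part B hypotheses using a 2.5% one-sided significance level" for Part B. Tables 10 and 11 list one equal-sized comparison per outcome, with 95 evaluable per group in Part A and 216 in Part B. The final allocation is 120 in Groups 1 and 2 and 240 in Groups 3–5. Of Group 3, 120 continue to the Part A vaccinations.

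**The concern.** Part A has two anti-S strains plus anti-gE, so two schedules give 2 × 3 = 6 comparisons. Part B has three HAI strains plus anti-gE, giving 2 × 4 = 8. The rule speaks of a single GMR and links the schedules with the word or. Three decision rules therefore fit the text, and they differ in power, in type I error and in what a success would mean.

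This rule decides whether each part of the trial succeeds. If it is still open when the results are known, the most favourable version can be chosen. Meanwhile section 13.1 claims 80% power for all hypotheses of each part from a calculation that appears to count one schedule.

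**Working it through.** **Inputs (section 13.1, Tables 10 and 11).** One-sided alpha 0.025; true GMR 1; margin 0.174 on log10. SDs are 0.35 for anti-S and anti-gE, and 0.45, 0.54 and 0.57 for H3N2, H1N1 and B Victoria. Evaluable per group: 95 (A) and 216 (B). At the final 120 per group with 10% dropout, Part A has 120 × 0.9 = 108 evaluable.

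**Assumptions, because the documents give no values.** Anti-S strain correlation 0–0.9. A common HAI correlation of 0.15–0.2, chosen because it returns about the stated 80.7%; 0–0.5 is shown as the wider range. Anti-gE is independent of the other endpoints.

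**1. Reproducing the stated power.** Power per test = Φ(0.174 / (SD × √(2/n)) − 1.96).
- Part A, n = 95: SE = 0.35 × √(2/95) = 0.0508, and Φ(3.426 − 1.960) = 0.9287. Cubed, this is 0.801, the stated 80.1%. The square (0.863) and the sixth power (0.642) do not match. The table therefore counts both anti-S strains and anti-gE, for one co-administration group.
- Part B, n = 216: 0.980, 0.918 and 0.887 for HAI, and 0.9993 for anti-gE. The stated HAI figure gives 0.807 × 0.9993 = 0.806, the stated 80.6%. This too is one group.

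**2. Both schedules must pass.** Two equal groups sharing a control have test statistics correlated 0.5.
- Part A, per endpoint: 0.8775 at n = 95 and 0.920 at n = 108. With uncorrelated strains, 0.8775³ = 0.676 and 0.920³ = 0.779.
- Part A by simulation over strain correlation 0–0.9: about 68–74% at 95 evaluable and 78–82% at 108.
- Part B by simulation at 216 evaluable: about 68–69% with 216 anti-gE controls. By Table 3, only Group 1 receives both RZV doses without C19 or aQIV, so the RZV-alone control is nearer 108. Anti-gE power is then 98.8% rather than 99.93%, and the both-pass figure is about 67–68%. Over HAI correlation 0–0.5 and either control size, the range is about 66–72%.

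**3. Either schedule suffices.** Power is above 90% in both parts. With both groups at the margin on one endpoint, error is 1 − P(Z₁ < 1.96, Z₂ < 1.96; correlation 0.5) = 0.045 (0.046 by simulation). At part level, with one endpoint at the margin in both groups and the rest at GMR 1, it is 4.0% (A, 95 evaluable) and 4.4% (B). The claim is 2.5%.

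**4. Schedules pooled.** Error stays at 2.5%. Power is about 93–97% in Part A (95 to 108 evaluable) and 92–93% in Part B. The comparison is then 2:1, not the 1:1 in the tables. As a single-endpoint illustration of masking, take true GMRs of 0.60 and 1.00. The mean log10 ratio is −0.222/2 = −0.111, and with 108 controls SE = 0.35 × √(1/108 + 1/216) = 0.0412. The pooled test passes with probability Φ((0.174 − 0.111)/0.0412 − 1.96) ≈ 0.33.

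**5. One schedule alone.** Part A at 108 evaluable: 0.9548³ = 0.870, rising to about 0.90 at strain correlation 0.9. Part B: about 80%.

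**The case against.** A reader might infer that the stated power or error is wrong whatever the rule. The documents do not support that. Under pooling, error is 2.5% and power exceeds 80%, and the singular wording of section 4.1 leaves pooling open. Against pooling stand the equal group sizes in Tables 10 and 11 and the reference in section 4.1 to ratios between groups, in the plural. Neither settles the matter.

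A reader might also take 68% as the Part A power. That figure belongs to 106 per group, a size the trial does not use. At 120 per group the strictest rule gives close to 80%, and it gives about 82–85% if loss stays at the 5% upper limit expected in section 12.6 (114 evaluable). Two strains measured in the same serum are also unlikely to be uncorrelated. Part B has no such reserve: 240 is already its final size, and 5% loss would raise the both-pass figure only to about 72%.

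It is tempting to argue that pooling defeats the rationale in section 2, which singles out the second RZV dose. That passage asks for safety data, and the safety outcomes are descriptive with their own first-dose and second-dose comparisons. It does not bear on how the GMRs are combined.

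Finally, the 4.5% error and the 33% masking probability are per endpoint and should not be read as part-level rates. Requiring both schedules is one valid rule among several. What stands is that the protocol fixes none of them, and that its power statement for all hypotheses rests on one schedule.

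**Conclusion.** The point holds as an undecided primary decision rule combined with a power statement that counts one of two schedules. The one-group basis of 80.1% and 80.6% is established by exact reproduction.

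The consequence depends on the rule chosen. Requiring both schedules leaves Part B at about 67–69% and Part A near its target at the enrolled size. Accepting either inflates the one-sided error to about 4.0–4.6%. Pooling preserves error and power but answers a different question, with a 2:1 comparison that the tables do not describe. The figures rest on the stated SDs, a true GMR of 1 in both schedules, a shared control and the assumed correlations. A later analysis plan could choose a rule, but the wording of section 13.1 would still need correcting if both schedules are to be shown non-inferior.

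**What to change.** Before any comparative analysis, state the rule in section 4.1 and align section 13.1 with it. The rule that best fits the tables' equal group sizes is a separate 95% confidence interval for each schedule:
- anti-S: Group 2 v 1 and Group 3 v 1;
- HAI: Group 4 v 3 and Group 5 v 3;
- anti-gE: each co-administration group v a named RZV-alone control, which by Table 3 can only be Group 1 if both doses must be given without C19 or aQIV.

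A schedule is non-inferior only if all its endpoints pass, and a part succeeds only if both schedules pass. Because every test must succeed, no alpha adjustment is needed.

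Restate power per schedule as about 87–90% (A, 120 per group) and 80% (B), and for both schedules as about 78–82% (A) and 67–69% (B), with the correlations assumed. If the sponsor prefers pooling or an either-schedule rule, state that and match the power and alpha to it.

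The cost is wording in the protocol and the analysis plan, and a less favourable stated power for Part B. No extra participants need be enrolled.

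### Table 11 powers the part B anti-gE comparison on 216 RZV-alone controls, but the design supplies about 108 (Group 1): anti-gE power is 98.8%, not 99.93%, and part B conjunctive power about 79.7%, not 80.6%

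*Protocol*

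**What the plan says.** Protocol section 13.1 sets the second part B hypothesis as "immunogenicity (anti-gE Ig concentrations) of concomitant administration of RZV (first or second dose) and aQIV will be non-inferior to RZV alone". The Table 11 row for it reads "Anti-gE Ig 216 0.35 1 0.174 99.93" (evaluable per group, SD on the log10 scale, true GMR, margin on the log10 scale, power in percent). The same 216 is used for the three HAI strains. Their joint power is stated as 80.7%, and part B overall as 80.6%. The text then concludes "A sample size of 240 per group will provide 80% power to test all part B hypotheses", at a one-sided 2.5% level and "allowing for 10% dropout".

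The final allocation is "120 into groups 1 and 2, 240 into groups 3-5, after inflating to fit a 1:1:2:2:2 allocation ratio". Section 4.1 defines the part B endpoint as "Anti-gE Ig concentrations expressed as GMCs after co-administration of aQIV/RZV (first or second dose) and RZV alone, 1 month after 2nd dose of RZV". It gives group numbers for the anti-S and HAI endpoints but none for anti-gE. The success criterion is that co-administration is "non-inferior to RZV alone if the lower limit of the 95% confidence interval for the GMR of Anti-gE Ig concentrations exceeds 0.67".

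**The concern.** The anti-gE comparison needs a group in which neither RZV dose was given with another vaccine. Table 3 (section 5.5) shows which groups qualify:

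- Group 1: RZV with placebo at day 56, then RZV at day 112. Neither dose is co-administered.
- Group 2: second dose given with C19.
- Group 3: first dose given with C19, and only 120 of its 240 participants go on to receive RZV.
- Group 4: first dose given with aQIV.
- Group 5: second dose given with aQIV.

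Only Group 1 qualifies, and it has 120 participants. The 240-participant control in part B is Group 3, which is the aQIV-alone control for HAI. Table 11 therefore powers the anti-gE comparison on a control arm twice the size of the one the trial randomises. At stake are the accuracy of two stated power figures and clarity about which group is the comparator in a confirmatory success criterion.

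**Working it through.** **Inputs.** From Table 11 (section 13.1): SD 0.35, margin 0.174 (which is −log10 of 0.67), true GMR 1, and HAI conjunctive power 80.7%. From the text of section 13.1: one-sided 2.5% level, 10% dropout, and groups of 120 or 240. Evaluable numbers are 240 × 0.9 = 216 and 120 × 0.9 = 108.

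**Formula.** SE = SD × √(1/n₁ + 1/n₂); power = Φ(0.174/SE − 1.96).

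**Step 1: reproduce the plan's figures (216 v 216).**
- SE = 0.35 × √(1/216 + 1/216) = 0.0337.
- 0.174/0.0337 − 1.96 = 3.206 (unrounded SE), and Φ(3.206) = 99.93%, as stated.
- The same formula returns 98.0%, 91.8% and 88.7% for the three HAI strains, also as stated.
- Conjunctive: 0.807 × 0.9993 = 80.6%, as stated.

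So the table used equal arms of 216 for anti-gE and multiplied the HAI and anti-gE powers.

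**Step 2: use the control arm the design provides (108 v 216).**
- SE = 0.35 × √(1/108 + 1/216) = 0.0412, which is 22% larger.
- 0.174/0.0412 − 1.96 = 2.258 (unrounded SE), and Φ(2.258) = 98.8%. A noncentral t calculation also gives 98.8%.
- Conjunctive: 0.807 × 0.988 = 79.7%.

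**Step 3: vary what the protocol leaves open.** HAI is held at 80.7%, because the correlation matrix behind it is not in the protocol.

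| Case | Anti-gE power | Part B conjunctive |
|---|---|---|
| As stated, 216 v 216 | 99.93% | 80.6% |
| One co-administration group v Group 1, 216 v 108 | 98.8% | 79.7% |
| Groups 4 and 5 must each pass v Group 1 (correlation 216/324 = 2/3) | 97.9% | 79.0% |
| Groups 4 and 5 pooled v Group 1, 432 v 108 | 99.6% | 80.4% |

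**Step 4: lower dropout.** Section 12.6 expects loss below 5%. At 5% the arms are 228 and 114, and anti-gE power is 99.1%. HAI power also rises, to 98.5%, 93.1% and 90.3%. If the strains are treated as independent, the product is 82.8%, and 0.828 × 0.991 = about 82%. Independence looks cautious here: at 216 per arm the independent product is 79.8%, below the protocol's 80.7%.

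**The case against.** A reader might infer that the 80% power claim for part B is false, or that part B is underpowered. The documents do not support that. The sentence in section 13.1 gives a rounded figure, and 79.7% still rounds to it. Which side of 80% the exact value falls on depends on whether Groups 4 and 5 are pooled, on actual dropout, and on an HAI figure that cannot be checked from the protocol. Across these cases the range is about 79% to 82%. HAI drives part B power, and anti-gE stays close to 98% or above throughout. Group 1's 108 also exceeds the 95 per arm that Table 10 shows is enough for 92.9% power on anti-gE with the same SD and margin.

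A reader might also object that the same 108 controls serve the anti-gE comparisons of both parts. A shared control is ordinary in a multi-arm trial. The two parts have separate success criteria, and sharing lowers neither part's power.

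Finally, one might want Group 1 named as the RZV-alone comparator throughout section 4.1. That would contradict the co-primary safety endpoints in the same section, which count RZV-alone doses from Groups 1 to 5. Single doses given alone do occur in the other groups. Only the two-dose anti-gE endpoint is confined to Group 1.

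All three objections stand as limits on the point. None removes the mismatch between the 216 in Table 11 and the 108 implied by Table 3 and the allocation.

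**Conclusion.** The point holds as an input and reporting error. Table 11's anti-gE row assumes a control arm of 216 where the design gives 108. Anti-gE power should read 98.8% instead of 99.93%, a drop of 1.1 points. Part B conjunctive power should read 79.7% instead of 80.6%, a drop of 0.9 points.

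These figures rest on the protocol's SD, margin, true GMR of 1 and 10% dropout, on its HAI conjunctive power of 80.7%, and on one co-administration group being compared with Group 1. If both groups must pass the figure is about 79.0%; if they are pooled it is 80.4%. The rounded 80% claim survives for practical purposes. Sample size, allocation and decision rule are unaffected.

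**What to change.** In Table 11, show the anti-gE row as 216 (Group 4 or 5) v 108 (Group 1), with power 98.8% and part B conjunctive power 79.7% (about 80%).

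In section 4.1, name Group 1 as the RZV-alone comparator for the anti-gE endpoint measured one month after the second RZV dose, in both parts. Limit that edit to this endpoint and leave the safety endpoints' use of RZV-alone doses from Groups 1 to 5 as it is.

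The cost is wording in the protocol, carried into the SAP where it repeats these figures. No change to recruitment or design follows.
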